1. OBJECTIVES

[figure not shown]
1.1 Primary

To characterize the pharmacokinetics of AMG 416 following thrice weekly intravenous (IV) administration of 5 mg in Chinese subjects with chronic kidney disease receiving hemodialysis.

1.2 Secondary

To characterize the safety and tolerability of AMG 416 following thrice weekly intravenous (IV) administration of 5 mg in Chinese subjects with chronic kidney disease receiving hemodialysis.

1.3 Exploratory

2. BACKGROUND AND RATIONALE

2.1 Disease

Secondary hyperparathyroidism occurs commonly among patients with chronic kidney disease (CKD), and it is an integral component of the syndrome of chronic kidney disease-mineral and bone disorder, or CKD-MBD. Persistently elevated levels of intact parathyroid hormone (iPTH) in serum or plasma are the cardinal biochemical feature of SHPT, affecting 40% to 50% of patients receiving dialysis regularly in the US ([USRDS 2009](#)). These biochemical changes are associated with abnormalities in bone histology, increased fracture risk, vascular and soft tissue calcifications, calciphylaxis, a variety of patient symptoms (eg, muscle weakness, fatigue, lethargy, bone and joint pain), and increased mortality ([USRDS, 2009](#); [Moe, 2001](#); [Diaz- Corte and Cannata-Andia, 2000](#); [Alem et al, 2000](#); [Block and Port, 2000](#); [Bro and Olgaard, 1997](#); [Salusky and Goodman, 1996](#); [Slatopolsky et al, 1980](#)).

Intact parathyroid hormone values not only serve as a useful index of disease severity, but also can be used to monitor evolution of the disorder over time and the response to treatment. The importance of managing SHPT chronically is highlighted in clinical practice guidelines promulgated by the National Kidney Foundation Kidney Disease Outcomes Quality Initiative (NKF KDOQI™) and the International Society of Nephrology Kidney Disease Improving Global Outcomes (KDIGO®) ([KDIGO, 2009](#); [K/DOQI, 2003](#)).

A retrospective study of Chinese hemodialysis patients during 2006 showed that mineral metabolism control in China remains an unmet medical need ([Kong, 2012](#)). Treatment

guidelines for SHPT cover several therapeutic strategies used to lower elevated serum iPTH levels and to manage SHPT among patients with CKD ([Saliba and El-Haddad, 2009](#); [KDIGO, 2009](#); [Locatelli et al, 2008](#)). Traditionally, most have employed treatment with vitamin D sterols such as calcitriol or other synthetic vitamin D analogues. Vitamin D therapies are only partially effective for controlling serum iPTH levels among patients with SHPT, and values often remain elevated despite ongoing treatment.

An alternative approach is directed toward enhancing signal transduction through modulation of CaSR in parathyroid tissue, thereby suppressing iPTH. These compounds are called calcimimetic agents, and they include cinacalcet, which is taken daily by mouth, and the investigational medication being evaluated in this study, AMG 416, which is administered intravenously three times per week (TIW) at the end of each hemodialysis treatment. Calcimimetics reduce iPTH secretion from the parathyroid glands and consequently lower serum iPTH levels. Reductions in serum calcium concentrations are also observed and are an expected physiological consequence of iPTH reduction. As such, treatment is initiated with small doses that are subsequently titrated upwards as needed to achieve meaningful reductions in serum iPTH levels only if serum calcium concentrations remain unchanged or decrease only modestly. Intact parathyroid hormone and corrected calcium (cCa) laboratory values are routinely drawn to measure the effectiveness of cinacalcet, and to titrate the dose as appropriate.

Detailed descriptions of the clinical studies of AMG 416 are provided in the [Investigator's Brochure](#).

2.2 Amgen Investigational Product Background

AMG 416 hydrochloride (formerly KAI-4169) is an 8-amino-acid peptide agonist of the calcium-sensing receptor (CaSR) being developed as an intravenous (IV) calcimimetic for the treatment of SHPT. The seven amino acids in the peptide backbone have an unnatural D-configuration which renders the peptide resistant to proteolysis. AMG 416 is administered to patients receiving hemodialysis as a bolus intravenous dose at the end of hemodialysis.

Refer to the [Investigator's Brochure](#) for additional information.

2.2.1 Nonclinical Experience

2.2.1.1 Nonclinical Pharmacology

AMG 416 has been shown in pharmacological studies to be a potent and selective allosteric activator of the CaSR, lowering the threshold of receptor activation by calcium,

the natural ligand. As such, it inhibits PTH secretion by the parathyroid tissue. The CaSR was shown in cellular studies to be the molecular target of AMG 416.

Please refer to the [Investigator's Brochure](#) for detailed descriptions of the nonclinical pharmacology of AMG 416.

2.2.1.2 Nonclinical Pharmacokinetics, Absorption, Distribution, Metabolism, and Excretion (ADME)

The intravenous administration of AMG 416 to rats and dogs with normal kidney function resulted in a dose-proportional plasma exposure with no evidence of significant accumulation. Renal elimination was the predominant in vivo clearance pathway in rats, with the administered dose excreted as intact AMG 416 or its biotransformed products. Significant biotransformation of AMG 416 occurred in whole blood, predominately via replacement of the L-cysteine moiety of AMG 416; the D-amino acid backbone of the molecule remained intact. A significant portion of administered AMG 416 was covalently bound via disulfide conjugation of the D-amino acid peptide backbone to serum albumin in rat and human plasma. Preliminary in vitro results indicate the covalent binding to serum albumin was reversible. The biotransformation of AMG 416 appeared to be the result of disulfide exchange rather than via conventional metabolism by enzymes such as cytochrome P450. This mechanism is in accord with the disposition of other thiol- or disulfide containing drugs, eg, captopril ([Duchin et al, 1984](#), [Narazaki et al, 1997](#)) and E-2072 ([Rais et al, 2012](#)). AMG 416 neither inhibited nor induced human hepatic cytochrome P450. AMG 416 was neither a substrate nor an inhibitor of common drug transporters.

Several low molecular weight disulfide biotransformation products formed by conjugation with endogenous thiols have been observed along with the albumin disulfide.

Tris(2-carboxyethyl) phosphine (TCEP) is a chemical agent that reduces disulfide bonds. TCEP reduction of plasma obtained from in vitro or in vivo studies resulted in the conversion of AMG 416 and all detected biotransformed products into a single component, M11 (the free thiol of the D-amino acid peptide backbone). Thus, M11 formed upon TCEP treatment of plasma is referred to as "Total M11" and is a measure of all AMG 416 related components with an intact D-amino acid peptide backbone.

Detailed descriptions of the pharmacokinetics (PK), distribution, metabolism, and excretion of AMG 416 in nonclinical species are provided in the [Investigator's Brochure](#).

2.2.1.3 Nonclinical Toxicology

AMG 416 is pharmacologically active in rats and in dogs, and all of the adverse effects observed in both species are related, either directly or indirectly, to the effect of AMG 416 on lowering serum calcium levels. There were no anatomic pathology findings or other effects that suggested off-target toxicity of AMG 416 unrelated to its mechanism of action. Moderate (13 to 17%) prolongation of the QTc interval was observed and related to peak reductions in serum calcium and not plasma drug concentrations. Results of the in vitro human Ether-à-go-go-Related Gene (hERG) assay suggest no direct effect of AMG 416 on the QT interval. The nonclinical data indicates that AMG 416 neither poses a genotoxic risk for humans nor affects fertility and embryo-fetal development.

For a complete list of completed safety studies and additional details about the results, please see the [Investigator's Brochure](#).

2.2.2 Clinical Experience

Etelcalcetide has been studied in three 26-week phase 3 studies, 2 placebo-controlled trials (20120229 and 20120230), and 1 active-controlled trial (20120360). In Study 20120229, 74% of etelcalcetide subjects achieved > 30% reduction from baseline in mean PTH during the efficacy assessment phase (EAP) versus 8.3% of placebo subjects ($p < 0.001$). In Study 20120230, 75.3% of etelcalcetide subjects achieved this endpoint versus 9.6% of placebo subjects ($p < 0.001$). Similarly, the proportion of etelcalcetide subjects who achieved mean predialysis PTH ≤ 300 pg/mL during the EAP was significantly higher in the etelcalcetide group than in the placebo group ($p < 0.001$) in both Studies 20120229 and 20120230. In Study 20120229, 49.6% of subjects in the etelcalcetide group and 5.1% of subjects in the placebo group achieved this endpoint, and 53.3% of subjects in the etelcalcetide group and 4.6% of subjects in the placebo group achieved this endpoint in Study 20120230. The events that occurred with a greater frequency among subjects in the etelcalcetide group compared with subjects in the placebo group ($\geq 5\%$ in the etelcalcetide group with $\geq 1\%$ difference from placebo) were blood calcium decreased (63.8% etelcalcetide; 10.1% placebo), muscle spasms (11.5% etelcalcetide; 6.6% placebo), diarrhea (10.7% etelcalcetide; 8.6% placebo), nausea (10.7% etelcalcetide; 6.2% placebo), vomiting (8.9% etelcalcetide; 5.1% placebo), headache (7.6% etelcalcetide; 6.0% placebo), and hypocalcemia (7.0% etelcalcetide; 0.2% placebo). An additional phase 3 study (20120360) was performed to compare the therapeutic efficacy of etelcalcetide and cinacalcet for lowering serum PTH

concentrations among subjects with CKD and SHPT receiving maintenance hemodialysis. A higher observed percentage of subjects in the etelcalcetide group (77.9%) had a > 30% reduction from baseline in serum PTH during the EAP compared with the cinacalcet group (63.9%). The estimated treatment difference (cinacalcet - etelcalcetide) was -10.48% (95% confidence interval [CI]: -17.45%, -3.51%). Because the upper bound of the 95% CI is < 12% (the prespecified margin for noninferiority), etelcalcetide is noninferior to cinacalcet in the proportion of subjects with a > 30% reduction from baseline in serum PTH during the EAP. Additionally, etelcalcetide was superior to cinacalcet on the proportion of subjects achieving a > 50% and a > 30% reduction from baseline in mean predialysis serum PTH during the EAP. There was no significant difference in the mean number of days of vomiting or nausea per week in the first 8 weeks of treatment, as measured by a patient-reported outcome instrument. The most common (> 10% in either treatment group) adverse events (etelcalcetide, cinacalcet) were asymptomatic decreased blood calcium (68.9%, 59.8%), nausea (18.3%, 22.6%), vomiting (13.3%, 13.8%), and diarrhea (6.2%, 10.3%). Symptomatic hypocalcemia was reported for 17 subjects (5.0%) in the etelcalcetide group and 8 subjects (2.3%) in the cinacalcet group. Please refer to the [Investigator's Brochure](#) for additional information.

2.2.2.1 Clinical Pharmacokinetics

After both single and repeat IV bolus administration in end stage renal disease (ESRD) patients, plasma AMG 416 exhibited a multiple exponential decay, characterized by rapid initial distribution followed by a prolonged log-linear elimination phase (Studies 20130139 and 20120330, respectively). Exposure (as assessed by mean C_{max} and AUC parameters) increased in a dose-related fashion.

In Study 20120330, AMG 416 was given at a dose of 5 or 10 mg three times a week (TIW) for 4 weeks (12 doses given IV at the end of dialysis to Cohorts 3 and 4). Repeated TIW dosing of AMG 416 was associated with modest accumulation as measured by plasma AMG 416 C_{max} and AUC_{last} ratios, mean C_{max} and AUC_{last} after twelve 5 mg doses were approximately 2-fold higher (C_{max}), and approximately 3-fold higher (AUC_{last}), relative to corresponding values on Study Day 1.

Population PK analysis was conducted using the PK data from patients receiving hemodialysis. A three-compartment PK model with non-specific linear elimination and linear dialysis elimination from the central compartment was deemed appropriate to describe the PK of AMG 416 after single and multiple IV administrations in subjects with

SHPT receiving hemodialysis. Within the dose range of 2.5 to 60 mg, no evidence of nonlinear elimination or time-dependent PK was observed. Dose-proportional increases in systemic exposures were observed.

Within the range of values evaluated, demographic factors (body weight, age, sex, race), liver function biomarkers (aspartate aminotransferase, alanine aminotransferase, serum albumin, total bilirubin), as well as baseline alkaline phosphatase, iPTH, cCa, phosphorus, serum creatinine, smoking status, and calcium supplements had no discernible impact on AMG 416 PK parameters. Consequently, further dose adjustments on the basis of these covariates are not warranted in subjects with SHPT receiving hemodialysis.

Ono Pharmaceuticals (ONO) conducted a comparative ethnic sensitivity study of the PK of AMG 416 in healthy Japanese and non-Asian subjects by comparing results at the matching dose levels (2 mg and 5 mg) from Amgen's Study 20130107 (n=12 non-Asian subjects) and Study ONO-5163-01 (n=12 Japanese subjects). ONO also conducted a comparative ethnic sensitivity study of the PK of AMG 416 in Japanese and non-Asian subjects receiving hemodialysis by comparing results from Amgen's Study 20130139 (n=11) and the ongoing Study ONO-5163-02 (n=12) at the matching dose levels (5 mg, 10 mg, and 20 mg). While these data are preliminary and do not represent full efficacy and safety comparisons, preliminary analysis of the data in healthy subjects and subjects with SHPT suggests that there are no significant differences in AMG 416 PK parameters between Japanese and non-Asian subjects.

Metabolism, Distribution and Excretion

AMG 416 does not undergo conventional metabolism (see [section 2.2.1.2](#)). The PK, biotransformation, and excretion, and elimination by hemodialysis of [¹⁴C] AMG 416 is currently being assessed in human hemodialysis subjects in study 20130147.

2.3 Risk Assessment

Safety reporting for all subjects in open-label and blinded studies completed as of 10 November 2017 and the investigators brochure have identified the following risks:
Important identified risks:

- Hypocalcemia
- Worsening heart failure
- QT prolongation secondary to hypocalcemia

Important potential risks:

- Ventricular arrhythmias
- Infusion and hypersensitivity reactions
- Convulsions (seizures)
- Adynamic bone
- Co-administration of cinacalcet (HCl) and etelcalcetide

The important identified risk is hypocalcemia, which will be mitigated in the protocol by close monitoring, and treatment as required. Coadministration of cinacalcet and AMG 416 is contraindicated until further studies inform the safety of simultaneous administration of these agents. The likelihood of these risks occurring with the planned dose for this study is expected to be low. In this study, cinacalcet will be prohibited from 30 days prior to informed consent and throughout the study.

Please refer to the [Investigator's Brochure](#), Section 7 for additional information for the investigator.

2.4 Rationale

The purpose of the current study is to characterize the PK, safety and tolerability of AMG 416 in Chinese subjects with chronic kidney disease receiving hemodialysis. This study will use a placebo-controlled dose of 5 mg AMG 416 administered IV at the end of dialysis thrice weekly for 4 weeks. Within the dose range of 2.5 to 60 mg, no evidence of nonlinear PK was observed. This design is similar to multiple dose Study 20120330 Cohort 3, conducted in non-Asian hemodialysis subjects (n = 12 at the 5 mg dose).

The 5 mg dose level, given thrice weekly for 4 weeks, was selected because it is the starting dose in the AMG 416 dose titration that is used in pivotal Phase 3 clinical trials, where dose may be adjusted every 4 weeks based on serum predialysis iPTH and cCa levels obtained in the prior week. The 5 mg dose was safe and well-tolerated in phase 2 studies and demonstrated a clinically meaningful effect on iPTH with approximately 50% of subjects achieving > 30% reduction in iPTH from baseline after approximately 4 weeks of dosing.

2.5 Clinical Hypotheses

This study will adequately characterize the PK profile of AMG 416 in Chinese subjects with chronic kidney disease receiving hemodialysis.

AMG 416 will be safe and well tolerated after multiple dose administration in Chinese subjects with chronic kidney disease receiving hemodialysis.

3. EXPERIMENTAL PLAN

3.1 Study Design

This is a multiple dose, double-blind, randomized, placebo-controlled clinical study. Chinese subjects residing in Mainland China with chronic kidney disease receiving hemodialysis will be randomized in a 3:1 ratio to receive 5 mg IV of AMG 416 or placebo thrice weekly (TIW) for approximately 4 weeks, with a subsequent follow up period of approximately 4 weeks.

Subjects will participate in the study as outpatients on scheduled study Day 1 through Day 55 (EOS) while receiving hemodialysis three times a week. All subjects, regardless of treatment assignment, will receive standard of care with calcium supplements, active vitamin D sterols, and phosphate binders, as prescribed by each individual Investigator. The overall study design is described by a [study schema](#) at the end of the protocol synopsis section.

The study endpoints are defined in [Section 10.1.1](#).

3.2 Number of Sites

This study will be conducted in Chinese subjects with chronic kidney disease receiving hemodialysis at multiple clinical sites in Mainland China.

3.3 Number of Subjects

Participants in this clinical investigation shall be referred to as “subjects”. Approximately 32 subjects are expected to participate in this study. Approximately 24 subjects are expected to receive AMG 416, and approximately 8 are expected to receive placebo. Refer to [Section 10.2](#) for the rationale for the number of required subjects.

3.4 Replacement of Subjects

Randomized subjects who miss AMG 416 or matching placebo doses may be replaced at the discretion of Amgen in consultation with the investigator or their designee. Subjects who drop out of the study may be replaced at the discretion of Amgen in consultation with the investigator or their designee.

Replacement subjects will receive the identical treatment as the assigned treatment for the subject to be replaced. All data from the replaced subjects will be captured and kept in the clinical trial database and identified as such.

3.5 Estimated Study Duration

3.5.1 Study Duration for Subjects

The estimated duration of study participation for each subject is approximately 77 days. This includes a 22-day screening period preceding a 55-day treatment and follow-up period. Subject participation may be adjusted based on treatment-emergent data. All adjustments or modifications to the schedule will be agreed upon by the investigator in consultation with Amgen. The institutional review board (IRB) will be informed via written correspondence and the informed consent form (ICF) will be updated accordingly.

3.5.2 End of Study

The end of the entire study for all subjects occurs at the primary completion time point.

Primary Completion: The time when the last subject is assessed or receives an intervention for the purposes of final collection of data for the primary analysis.

4. SUBJECT ELIGIBILITY

Investigators will be expected to maintain a screening log of all potential study candidates that includes limited information about the potential candidate (eg, date of screening). Before any study-specific procedure, the appropriate written informed consent must be obtained (see [Section 11.1](#)).

4.1 Inclusion Criteria

- 4.1.1 Subject has provided informed consent prior to initiation of any study-specific activities/procedures
- 4.1.2 Resident in Mainland China and of Chinese ancestry
- 4.1.3 Male or female subject ≥ 18 and ≤ 70 years of age at the time of screening, with end stage renal disease receiving hemodialysis
- 4.1.4 Body mass index is between 18 and 35 kg/m², inclusive
- 4.1.5 Subject must be receiving hemodialysis 3 times weekly for at least 3 months through a functioning permanent dialysis access prior to Day -2 and have adequate hemodialysis with a delivered Kt/V ≥ 1.2 or urea reduction ratio (URR) $\geq 65\%$ within 4 weeks to screening or at screening. The subject's routine hemodialysis session must be of 3-4.5 hours in duration, inclusive
- 4.1.6 Subject has stable dialysis prescription and this prescription is not anticipated to significantly change during the course of the study

4.2 Exclusion Criteria

- 4.2.1 Corrected calcium (calculated) level is < 2.07 mmol/L (8.3 mg/dL), and/or intact PTH level is outside the range of 31.8 – 127.2 pmol/L (300 - 1200 pg/mL) at screening and Day -2 (Day -2 assessments are only required if screening visit performed greater than 7 days prior to Day 1)
- 4.2.2 Chemistry and all other laboratory tests are not within clinically acceptable range to the investigator and sponsor at screening
- 4.2.3 Female subjects who are pregnant lactating/breastfeeding, or who plan to conceive, or breastfeed while on study through 3 months after receiving the dose of study drug
- 4.2.4 Female subject of reproductive potential not willing to use a(n) acceptable method(s) of effective birth control during treatment with AMG 416, and for an additional 3 months after the end of treatment with AMG 416. Female subjects who have had a hysterectomy, bilateral salpingectomy, bilateral oophorectomy, bilateral tubal ligation, or who are postmenopausal are not required to use contraception. Postmenopausal is defined as:
- Age > 55 years with cessation of menses for 12 months or more
 - Age < 55 but no spontaneous menses for at least 2 years
 - Age < 55 years and spontaneous menses within the past 1 years, but currently amenorrheic, AND with postmenopausal gonadotropin levels (luteinizing hormone and follicle-stimulating hormone levels > 40 IU/L) or postmenopausal estradiol levels (<5.3 pmol/L or 5 ng/dL) or according to the definition of “postmenopausal range” for the laboratory involved
 - Underwent a bilateral oophorectomy
- 4.2.5 Females of reproductive potential with a positive pregnancy test, unless medical follow-up confirms the subject is not pregnant
- 4.2.6 Positive for human immunodeficiency virus (HIV) at screening or known diagnosis of acquired immune deficiency syndrome (AIDS)
- 4.2.7 Positive Hepatitis B Surface Antigen (HepBsAg) at screening (indicative of chronic Hepatitis B)
- 4.2.8 Positive for Hepatitis C virus Ribonucleic acid (RNA) by Polymerase Chain Reaction (PCR) at screening (indicative of active Hepatitis C – screening is generally done by Hepatitis C Antibody (HepCAb), followed by Hepatitis C virus RNA by PCR if HepCAb is positive)
- 4.2.9 Previous administration of AMG 416
- 4.2.10 Subject has received cinacalcet within the 30 days prior to informed consent (treatment with cinacalcet is prohibited during the study)
- 4.2.11 Subject has known sensitivity to any of the products or components to be administered during dosing

-
- 4.2.12 Use of concomitant medication other than that used in the management of end stage renal disease and its expected comorbidities that could in the opinion of the investigator or Amgen medical monitor interfere with the safety of subjects or interpretation of study results
- 4.2.13 Use of any herbal medicine, vitamins, and supplements consumed by the subject within 30 days prior to the dose of investigational product and continued use, if appropriate, will be reviewed by the Principal Investigator and the Amgen Medical Monitor. Written documentation of this review and Amgen acknowledgment is required for subject participation.
- 4.2.14 Positive result for alcohol at Day -2, known alcohol or illicit drug abuse within 12 months of screening, unwilling or unable to refrain from alcohol consumption 24 hours in advance of each study visit, unwilling or unable to limit alcohol consumption to up to 2 drinks per day for the duration of the study during (1 drink being equivalent to 12 ounces of regular beer, 8 to 9 ounces of malt liquor, 5 ounces of wine, or 1.5 ounces of 80 proof distilled spirits).
- 4.2.15 Receiving or has received any investigational drug (or is currently using an investigational device) within the 30 days before receiving study drug, or at least 10 times the respective elimination half-life (whichever is longer)
- 4.2.16 Subject has lost 500 mL or more of blood or plasma within 8 weeks of study drug administration or during the study period
- 4.2.17 Anticipated or scheduled to have major surgical procedures during the study period such as kidney transplant or parathyroidectomy
- 4.2.18 Subject has an active infection at screening or Day -2, or a history of any illness that, in the opinion of the Investigator, might confound the results of the study or pose additional risk to the subject
- 4.2.19 History of malignancy within 5 years before Day -2 (except non-melanoma skin cancers, or cervical carcinoma in situ)
- 4.2.20 Subject's 12-lead electrocardiogram (ECG) at screening suggests unstable arrhythmia or other cardiac abnormality that could place the subject at increased risk, based upon the Investigator's opinion
- 4.2.21 Subject has current or history of cardiovascular conditions such as uncontrolled hypertension, symptomatic ventricular dysrhythmias, Torsades de Pointes, angina pectoris congestive heart failure (New York Heart Association Classification III or IV), myocardial infarction, coronary angioplasty, or coronary arterial bypass grafting within the past 6 months prior to screening
- 4.2.22 Subject is receiving treatment for a seizure disorder or has a history of a seizure within the last 12 months prior to screening
- 4.2.23 Subject has had major surgery (excluding hemodialysis access repair) within the last 8 weeks prior to screening
- 4.2.24 Subject likely to not be available to complete all protocol-required study visits or procedures, and/or to comply with all required study procedures to the best of the subject and Investigator's knowledge

4.2.25 History or evidence of any other clinically significant disorder, condition or disease that, in the opinion of the investigator or Amgen physician, if consulted, would pose a risk to subject safety or interfere with the study evaluation, procedures or completion

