- ^c Blood sample for PT and aPTT will be drawn prior to heparin administration for dialysis. Day 1 hematology and coagulation tests will be performed only if day 1 occurs more than 2 weeks after the screening hematology and coagulation tests.
- ^d Serum samples for albumin and calcium for screening and routine monitoring of predialysis cCa. When albumin is less than 4.0 g/dL, the calcium level will be corrected according to the formula: $cCa \text{ (mg/dL)} = \text{total Ca (mg/dL)} + (4 - \text{albumin (g/dL)}) \times 0.8$. Corrected calcium results will inform dosing/dose withholding at the next hemodialysis treatment.
- ^e Perform Kt/V or URR assessment at screening unless a qualifying Kt/V or URR measurement from within 4 weeks prior to screening assessments is available.
- ^f Serum samples for anti-drug antibodies will be collected predialysis on days 1, 29, and 55. Any subjects with positive titers for antibodies to AMG 416 may be asked to return to the clinical research unit to provide additional serum samples.
- ^g Luteinizing hormone and estradiol levels may additionally be collected if deemed necessary for confirmation of postmenopausal status as described in exclusion criteria [section 4.2.4](#)

Table 1c. Schedule of Pharmacokinetic Assessments

Time	Assessment	Study Visit (Day)																			
		Screening	-2	1 (HD)	2	3 (HD)	6 (HD)	8 (HD)	10 (HD)	13 (HD)	15 (HD)	17 (HD)	20 (HD)	22 (HD)	24 (HD)	27 (HD)	28	29/ ET ^a (HD)	34 (HD)	41 (HD)	55 (HD)
Central Laboratory																					
Pre HD	PK			X		X		X			X			X		X		X	X	X	X
SDA + 10 min	PK			X				X			X			X		X					
SDA + 30 min	PK			X												X					
SDA + 60 min	PK			X												X					
SDA + 90 min	PK			X												X					
SDA + 18 to 30 hr	PK				X												X				

HD = hemodialysis; ET = early termination; SDA = Study drug administration.

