7.3.10 Clinical Chemistry, Hematology

Blood samples for clinical chemistry and hematology will be collected at screening, the day -2, and the time points specified in the Schedule of Assessments.

The tests listed below in [Table 2](#), will be conducted on samples collected and analyzed by standard laboratory procedures.

Table 2. Chemistry, Hematology

Chemistry	Hematology	Other Labs
Sodium	Red blood cells	Antidrug Antibodies
Potassium	Hemoglobin	Hep B surface antigen
Chloride	Hematocrit	Hep C antibody
Total protein	Mean corpuscular volume	HIV
Albumin	Platelets	Pregnancy
Glucose (Random)	White blood cells	Intact PTH (iPTH)
Blood urea nitrogen	Differential	25-hydroxyvitamin D
Creatinine	• Total neutrophils	PK
Total bilirubin	• Eosinophils	PT
Direct bilirubin	• Basophils	aPTT
Alkaline phosphatase	• Lymphocytes	FSH ^b
Alanine aminotransferase (ALT)	• Monocytes	Luteinizing hormone ^b
Aspartate aminotransferase (AST)		Estradiol ^b
Calcium		Syphilis ^c
Adjusted Calcium		Urea/BUN ^d
Creatinine phosphokinase		
Phosphorus		
Thyroid-stimulating hormone (TSH) ^a		

^a Only required at screening for subjects who have a history of hyper- or hypothyroidism and do not have available TSH results within 6 months prior to screening

^b Females only, and only collected if deemed necessary for confirmation of postmenopausal status as described in exclusion criteria [section 4.2.4](#)

^c Only collected at screening when investigator consider it is necessary

^d Urea/BUN measurement to be performed locally for Kt/V or URR assessment at screening, unless a qualifying Kt/V or URR measurement from within 4 weeks prior to screening assessments is available.

All clinical chemistry and hematology tests must be reviewed, signed, and dated by the Investigator or qualified designee, and all abnormal values must have clinical significance assessed. Additional safety laboratory assessments may be performed, if clinically indicated.

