7.3.11 Follicle Stimulating Hormone Test (Females Only)

To confirm postmenopausal status for eligibility, a blood sample for the determination of serum FSH will be collected at screening and analyzed by standard laboratory procedures. To be eligible for this study, FSH results must be within or above the laboratory's reference range for postmenopausal. Serum FSH is required for subjects as described in exclusion criteria [section 4.2.4](#) (age < 55 years and spontaneous menses within the past 1 years, but currently amenorrheic).

7.3.12 Human Immunodeficiency Virus Antibodies, Hepatitis B Surface Antigen, and Hepatitis C Antibodies

Human immunodeficiency virus 1 and 2 antibodies, HBsAg, and HepCAb titers will be assessed at screening. Serology tests must be negative in order for a subject to be eligible for the study.

7.3.13 25-hydroxy Vitamin D

The 25-hydroxy vitamin D will be obtained at screening as a part of the clinical chemistry sample. Subjects with a 25-hydroxyvitamin D level < 20 ng/mL can be repeated at the Investigator's discretion. Amgen will not provide or reimburse for vitamin D supplements.

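### The postmenopausal estradiol limit in Protocol 4.2.4 is printed in two units that differ about 35-fold

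*Protocol*

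**What the plan says.** Protocol 4.2.4 excludes women of reproductive potential who will not use effective contraception during treatment and for 3 months afterwards. Postmenopausal women are exempt, and the section defines the term. For women under 55 with spontaneous menses within the past year who are now amenorrheic, it offers three routes joined by *or*:

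- "postmenopausal gonadotropin levels (luteinizing hormone and follicle-stimulating hormone levels > 40 IU/L");
- "postmenopausal estradiol levels (<5.3 pmol/L or 5 ng/dL");
- "or according to the definition of “postmenopausal range” for the laboratory involved".

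The test is conditional. Footnote g to Table 1b says "Luteinizing hormone and estradiol levels may additionally be collected if deemed necessary for confirmation of postmenopausal status", and footnote b to Table 2 (section 7.3.10) says of these hormones "Females only, and only collected if deemed necessary for confirmation of postmenopausal status". Both footnotes refer the site back to 4.2.4. Section 7.3.11 makes FSH the mandatory test for this subgroup: "Serum FSH is required for subjects as described in exclusion criteria" 4.2.4.

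No other section of the Protocol, and nothing in the SAP, gives or corrects an estradiol limit.

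**The concern.** The bracket reads as one threshold given in SI and conventional units, as 4.2.1 does for corrected calcium and iPTH. If so, the two numbers must convert into each other, and they do not.

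What is at stake is the classification of individual women. If 5 ng/dL is the intended level, a site whose laboratory reports in pmol/L would apply a limit that is far too strict, and a woman who is postmenopausal by the intended rule would be required to use contraception or be excluded for declining it. If a much lower level was intended, 5 ng/dL is too lenient and would exempt women who should not be exempt. The Protocol does not say which is meant, so the outcome could depend on the units the laboratory happens to use.

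**Working it through.** **Inputs**

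- Printed limits, Protocol 4.2.4: 5.3 pmol/L and 5 ng/dL.
- Molar mass of estradiol, M: not in the documents. Assumed from the formula C18H24O2: 18 × 12.011 + 24 × 1.008 + 2 × 15.999 = 272.388 g/mol. Range shown: 270 to 275 g/mol.
- iPTH range, Protocol 4.2.1: "31.8 – 127.2 pmol/L (300 - 1200 pg/mL").
- Corrected calcium limit, Protocol 4.2.1: 2.07 mmol/L, given as 8.3 mg/dL.

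**Step 1. Conventional to SI.** 5 ng/dL × 10 = 50 ng/L = 50 pg/mL. Then pmol/L = (pg/mL ÷ M) × 1000.

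| M (g/mol) | 5 ng/dL in pmol/L | Ratio to 5.3 pmol/L | 5.3 pmol/L in ng/dL |
|---|---|---|---|
| 270 | 185.2 | 34.9 | 0.143 |
| 272.388 | 183.6 | 34.6 | 0.144 |
| 275 | 181.8 | 34.3 | 0.146 |

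The last column is the reverse conversion, 5.3 × M ÷ 10,000. The printed pair is not reproduced in either direction.

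**Step 2. Could a unit have been misprinted?** If the second figure were 5 pg/mL, it would equal 18.4 pmol/L, still 3.5 times 5.3. If it were 5 ng/mL, it would be about 18,356 pmol/L, roughly 3,460 times 5.3. Neither reconciles the pair.

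**Step 3. Are the other dual-unit limits in this section consistent?** Calcium: 8.3 mg/dL × 10 ÷ 40.078 = 2.071 mmol/L, which matches the printed 2.07. iPTH: 31.8 ÷ 300 = 0.106 and 127.2 ÷ 1200 = 0.106, the same factor at both ends. Paired units elsewhere in 4.2 are therefore meant as equivalents.

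**Step 4. A possible origin.** The estradiol pair would agree only if M were 50 ÷ 5.3 × 1000 = 9,434 g/mol. The iPTH pair implies exactly that molar mass: 300 ÷ 31.8 × 1000 = 9,434 g/mol. Equivalently, 50 × 0.106 = 5.3. The pmol/L figure is what results from applying the iPTH factor to estradiol. This is an inference from the arithmetic; the documents do not state it, and the mismatch does not depend on it.

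**Step 5. Where the two limits disagree.** On the estradiol route alone, they classify a woman differently when her value lies between 5.3 and about 184 pmol/L (about 0.14 to 5 ng/dL).

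**The case against.** The strongest objection concerns importance, not arithmetic. For the wrong figure to matter, a woman must be in the narrow subgroup, have had the optional estradiol test, not have been settled by gonadotropins or by the laboratory's range, and have been judged on the pmol/L figure. The trial plans about 32 subjects of both sexes, and the documents do not say how many would fall in that subgroup. If 5 ng/dL is the intended level, the error is also on the cautious side, since it leads to unneeded contraception and not to added pregnancy risk. Protocol 2.2.1.3 reports no nonclinical effect on fertility or embryo-fetal development, and pregnancy tests are scheduled in any case. All of this stands, and it keeps the point small.

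A second objection is that the figures are joined by *or*, so a woman below 5 ng/dL meets the bracket whatever the pmol/L figure says. This does not rescue the text. Any value below 5.3 pmol/L is also below 5 ng/dL, so on that reading the first number does nothing. The pair makes sense only as one level in two units.

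A third is that the iPTH explanation cannot be verified. That is correct, and it should not be counted as evidence of the error.

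**Conclusion.** The concern holds. The two printed estradiol limits differ by a factor of 34.6 at 272.4 g/mol, and of 34.3 to 34.9 over 270 to 275 g/mol. The only outside input is the molar mass of estradiol, and the result barely moves over that range.

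This is a wrong decision threshold in the contraception rule, so it should be corrected, but its practical effect is limited to a few women at most and may be nil. Which of the two numbers is wrong is not settled by the documents.

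**What to change.** Ask the sponsor to confirm the intended level. If it is 5 ng/dL, change 5.3 pmol/L to about 184 pmol/L. If not, or if no fixed number is wanted, delete both figures and rely on the laboratory's postmenopausal range, which 4.2.4 already accepts.

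Two wording changes could go into the same edit, though neither is a separate error: assign age exactly 55 to one of the age bands in 4.2.4, which now run above 55 and below 55, and make clear in 7.3.11 that the FSH result determines menopausal status.

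The cost is one line in a clarification memo or the next amendment, with no new procedure, sample or analysis.
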